Large retrospective, prospective, and observational trials have also been conducted, mostly outside of the United States. These studies report measurable clinical markers: **maternal markers** include rate of spontaneous vaginal birth (SVD), rate of cesarean section, length of labor, blood loss, use of pharmacological or anesthetic analgesia, and perineal lacerations; **neonatal markers** include Apgar score, admission to neonatal intensive care (NICU), respiratory distress, and rate of infection. The most controversial aspect of waterbirth is the unknown risks and/or benefits to the neonate. Several studies and meta-analyses have focused entirely on neonatal outcomes. One systematic review and meta-analysis included only data from hospital births and found no increased risk to the neonate; however, there is significant heterogeneity among the included studies.

Despite the current body of literature, there are many limitations to use of the above studies in the United States. The authors of the Cochrane review note that studies are not comparable and there were wide protocol and data collection variations. Moreover, the studies come from a wide

variety of countries and health systems, which limits their generalizability and applicability in the United States. Researchers estimate that approximately 6-15% of US hospitals offer waterbirth.

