## II. SPECIFIC AIMS

The proposed pilot randomized control trial will be approached as a feasibility study to explore or test (if sample size permits) our hypotheses. Additional sample size analyses have been conducted since this study was first submitted as we continue to explore the feasibility of this study in hopes of answering our primary outcome.

**Primary outcome:** Women in the waterbirth group will use less IV narcotic and epidural anesthesia than women in the land birth group.

We further seek to address the following additional specific aims:

**Specific Aim 1:** Evaluate waterbirth outcomes in adult low-risk laboring women randomized to waterbirth in comparison to women randomized to birth on land.

**Hypothesis 1a.** Women in the waterbirth cohort will have shorter labor duration than women in the land cohort.

**Hypothesis 1b.** Women in the waterbirth cohort will be more likely to initiate breastfeeding before discharge.

**Specific Aim 2:** Evaluate the safety of waterbirth in adult low-risk laboring women randomized to waterbirth in comparison to women randomized to birth on land.

**Hypothesis 2a.** Women in the waterbirth cohort will not experience more adverse outcomes (e.g., postpartum hemorrhage, third- or fourth-degree perineal lacerations, etc.) than women in the control group.

**Specific Aim 3:** Evaluate satisfaction with waterbirth in adult low-risk laboring women randomized to waterbirth in comparison to women randomized to birth on land.

**Hypothesis 3.** Women in the waterbirth cohort will experience greater satisfaction scores on the revised United States Birth Satisfaction Scale-Revised (US-BSS-R), than women in the land cohort.

**Specific Aim 4:** Evaluate the safety of waterbirth for term low-risk neonates in comparison to land birth term low-risk neonates.

**Hypothesis 4a.** Infants in the waterbirth group will not experience more adverse outcomes (e.g., NICU admission, APGAR scores <7, umbilical cord injury, etc.) than infants born to women in the land cohort.

**Hypothesis 4b.** Infants in the waterbirth group will experience fewer instrumental (e.g., forceps, vacuum, etc.) or cesarean deliveries.

**Hypothesis 4c.** Infants born to women in the waterbirth cohort will have immediate skin-to-skin contact.

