### **D. Evaluation and care of the neonate**

a.) The neonatal resuscitation (NRP) guidelines of the American Heart Association should be utilized to assess the neonate and Apgar scores should be obtained at one and 5 minutes after birth per routine. If neonatal resuscitation measures are indicated and this is not possible without cutting the cord, the cord should be clamped and cut, and the neonate removed from the water immediately.

b.) Make certain the neonate remains close to the woman (skin-to-skin) and partially submerged to help maintain body temperature. Dry the neonate's exposed head to reduce heat loss.

c.) If neonatal tachycardia (heart rate greater than 160 bpm), bradycardia (heart rate less than 100bpm), hyperthermia (temperature greater than 38°C [100.4°F]), hypothermia (temperature less than 36°C [97.0°F]), tachypnea (respirations greater than 60 per min), grunting, or retracting is noted, the neonate should be moved to the infant warmer for further assessment, per routine unit standards.

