  - o. Quantified blood loss (QBL calculation begins after the delivery of the placenta using the blue bag; clots, linens, and lap sponges will be weighed. Unit protocol will be followed. Hemorrhage QBL  $\geq$  1,000 mL)
  - p. Was patient switched from waterbirth to land birth?
    - a. Why?

- q. Was patient switched from any birth to cesarean or operative delivery?
    - a. Why?
    - b. Cesarean (0=No; 1=Yes)
    - c. Instrumental delivery (0=No; 1=Yes)
      - i. Forceps (0=No; 1=Yes)
      - ii. Vacuum (0=No; 1=Yes)
  - r. Labor duration and time (by phase: first, second, third)
    - a. Induction (0=No; 1=Yes)
    - b. Spontaneous labor (0=No; 1=Yes)
  - s. Dilation at time of admission of birth
  - t. Medications used (analgesia and anesthesia) (0=No; 1=Yes)
    - a. Epidural (0=No; 1=Yes)
      - i. Epidural eligibility (0=No; 1=Yes)
    - b. Spinal epidural (0=No; 1=Yes)
    - c. IV narcotic medication (Nubain or Stadol) (0=No; 1=Yes)
  - u. Maternal complications (0=No; 1=Yes)
    - a. Laceration (1st, 2nd, 3rd, 4th degree)
      - i. Episiotomy (0=No; 1=Yes)
    - b. Shoulder dystocia (0=No; 1=Yes)
  - v. Maternal satisfaction (US-BSS-R, modified)
    - a. Postpartum day survey was completed (0=PPD0; 1=PPD1; 2=PPD2; 3=PPD3)
  - w. Was breastfeeding initiated at any point prior to discharge? (0=No; 1=Yes)
  - x. Date and time of discharge
    - a. Length of hospital stay
3. *Newborn variables*
- a. Date and time of skin-to-skin contact
    - a. Time from birth to skin-to-skin contact
  - b. One- and five-minute APGAR scores
  - c. Were there any newborn complications at time of birth? (0=No; 1=Yes)
    - a. If yes, newborn complications including:
      - i. NICU admission (0=No; 1=Yes)
        - 1. If yes, NICU admission and discharge date for LOS
      - ii. Infection (0=No; 1=Yes)
      - iii. Injury (0=No; 1=Yes)
      - iv. Cord injury (0=No; 1=Yes)
      - v. Other (0=No; 1=Yes)
        - 1. What?
  - d. If available, Cord Ph (arterial and venous)
  - e. At approximately 4-8 weeks postpartum, coordinator follow-up regarding newborn status (at postpartum visit or via phone call, etc.)
    - a. Were we able to touch base (0=No; 1=Yes)
    - b. If yes, were there any neonatal complications since discharge? (0=No; 1=Yes)
    - c. If any complications since discharge?
      - i. Neonatal hospital admission (0=No; 1=Yes)
        - 1. If yes, follow-up comments

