## VIII. POTENTIAL RISKS AND BENEFITS

Potential risks associated with any vaginal delivery regardless of study participation:

- Maternal risks including infection and all risks associated with vaginal delivery including but not limited to hemorrhage, laceration, sepsis, and other rare maternal morbidity and mortality
- Neonatal risks associated with vaginal delivery including but not limited to infection, sepsis, water inhalation, umbilical cord avulsion, respiratory distress, low APGAR scores, NICU admission, and rare adverse neonatal morbidity and mortality including neonatal death

Potential benefits although unknown:

- Maternal benefits may include improved pain control, fewer obstetric lacerations, increased comfort during labor, increased mobility, and ease of delivery positioning due to increased buoyancy, improved relaxation, a more satisfying birth experience, increased perception of control, decreased cesarean delivery, and an additional option for pain control in a hospital setting in the Milwaukee area.
- Neonatal benefits may include less exposure to maternal pain medication/narcotic use, fewer interventions in labor, fewer instrumental and cesarean deliveries, immediate skin-to-skin contact with improved infant maternal bonding, and fewer NICU admissions.

Waterbirth is considered by ACOG/AAP to be an experimental procedure and, therefore, not all risks and benefits are known. It is considered a beneficial option for low-risk healthy women by the American College of Nurse Midwives and the Royal College of Obstetricians and Gynecologists/Royal College of Midwives. Providers who participate in the study will receive standardized training for waterbirth and will be in compliance with our internal Institutional Review Board research guidelines. Nursing staff will receive training by the study PI and co-investigators.

If our pilot study shows that waterbirth is a reasonable option for low-risk healthy women, we will seek to implement a larger, multi-center trial on the labor and delivery floor at Aurora Sinai Medical Center and at other Advocate Aurora hospitals. Additionally, we seek to publish and disseminate our findings so that other hospitals can adopt our protocols. Lastly, we also seek to model interdisciplinary collaboration between obstetrics, midwifery, and neonatology to offer this service.

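### Neonatal respiratory distress and resuscitation have no coded data item, so mild events can go unrecorded in either arm and the open-ended part of Hypothesis 4a is weakly measured

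*Combined protocol and SAP*

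**What the plan says.** Hypothesis 4a (section II, Specific Aims) reads: "Infants in the waterbirth group will not experience more adverse outcomes (e.g., NICU admission, APGAR scores <7, umbilical cord injury, etc". The list is given as examples and left open.

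Section I (Background and Significance) lists the neonatal markers reported by earlier studies: "Apgar score, admission to neonatal intensive care (NICU), respiratory distress, and rate of infection". Section VIII (Potential Risks and Benefits) gives: "Neonatal risks associated with vaginal delivery including but not limited to infection, sepsis, water inhalation, umbilical cord avulsion, respiratory distress". Section V.D, on care of the neonate, names bedside signs: "tachypnea (respirations greater than 60 per min), grunting, or retracting is noted, the neonate should be moved to the infant warmer". The same paragraph gives heart-rate and temperature limits.

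In the Newborn variables of section VII (Data Collection), item (c) starts with one question: "Were there any newborn complications at time of birth? (0=No; 1=Yes". Below it comes "If yes, newborn complications including", followed by NICU admission, infection, injury, cord injury and "v. Other (0=No; 1=Yes" with a text field for what it was. Three further sources lie outside that question: "One- and five-minute APGAR scores", cord pH where available, and a coordinator contact at about 4-8 weeks covering hospital admission, infection and other complications.

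**The concern.** Section I calls the unknown effect on the neonate the most controversial aspect of waterbirth. Of the four neonatal markers it lists, Apgar, NICU admission and infection each have a data item; respiratory distress does not. Cord avulsion, another risk in section VIII, is covered by the cord injury item, so the form does provide for some of the named risks.

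Hypothesis 4a claims no excess of harm. For a claim of that kind, missed events tend to support the conclusion the investigators hope for. A newborn with brief grunting or fast breathing, settled at the warmer, may have a normal five-minute Apgar and no NICU stay. Whether that event appears in the data depends on whether someone regards it as a complication, a word the plan does not define.

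The pilot is also meant to inform a larger trial and contribute to meta-analyses (sections III and VII, Statistical Plan). Without a coded item it cannot reliably supply a marker that its own background section treats as standard.

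**Working it through.** The documents state no figure on this point. The check sets the neonatal events that the protocol names against the items it collects.

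| Event | Where the protocol names it | Item in section VII |
|---|---|---|
| Low Apgar | I, II (4a), VIII | Yes, every newborn, outside the complications question |
| NICU admission | I, II (4a), VIII | Yes, under the complications question |
| Infection | I, VIII | Yes, under the complications question and at 4-8 weeks |
| Cord injury or avulsion | II (4a), VIII | Yes, under the complications question |
| Respiratory distress | I, VIII; signs in V.D | None; Other plus text |
| Resuscitation | V.B and V.D, as an action | None; Other plus text |
| Water inhalation | VIII | None; Other plus text |
| High or low temperature | V.D only | None; Other plus text |

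1. All three outcomes named in Hypothesis 4a have an item. The gap concerns what the hypothesis leaves open.

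2. Severe respiratory events should show through NICU admission, Apgar, cord pH where taken, or readmission at follow-up, though without a cause. Mild or transient ones may show nowhere else, so for them the Other item is the only dependable route.

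3. Effect of equal under-recording. The inputs are assumed, because the documents give no event rate and no capture rate. The group sizes of 74 and 37 are the numbers needed for the epidural comparison in the Statistical Plan. Expected recorded events = births × true rate × capture.
   - True rate 5%, full capture: 74 × 0.05 = 3.7 and 37 × 0.05 = 1.85.
   - True rate 5%, 60% capture in both arms: 3.7 × 0.6 = 2.22 and 1.85 × 0.6 = 1.11.
   - True rate 10%: 7.4 and 3.7 with full capture; 4.44 and 2.22 with 60% capture.

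4. Effect of unequal recording, if there were any. Observed risk ratio = true risk ratio × (capture in water ÷ capture on land).
   - Capture 90% water, 50% land, true ratio 1.0: 0.90 ÷ 0.50 = 1.8.
   - Capture 50% water, 90% land, true ratio 1.0: 0.50 ÷ 0.90 = 0.56.
   - Capture 50% water, 90% land, true rates 10% and 5% (ratio 2.0): 0.10 × 0.50 = 5.0% against 0.05 × 0.90 = 4.5%, a ratio of 1.11.

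   These ratios follow directly from the capture rates put in. They show that the distortion could run either way, not that it exists.

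5. Grounds for thinking recording could be unequal: the birth setting is plain to staff, and the initial safety review in Appendix D covers only the first ten completed waterbirths and their infants. Its table words the purpose of the continued review in terms of waterbirth as well. Nothing in the documents shows what effect this has on recording.

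**The case against.** The best defence is that the plan collects more than item (c) suggests. Every outcome Hypothesis 4a names is coded. Apgar scores are taken for all newborns, and cord pH and the 4-8 week contact add to them. The Other item is itself a prompted yes/no; only the type of event is text. The data come largely from the Epic delivery record, so a charted event can still be retrieved. The trial is a pilot that will test its hypotheses only if numbers allow. All of this stands, and it confines the gap to mild or transient events and to the unnamed part of the hypothesis.

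A reader might go further and infer that the Hypothesis 4a comparison is biased because waterbirth infants are watched more closely. The documents do not support that. Section V.D refers warmer assessment to the unit's usual standards, and section VI puts land births under routine care, so different assessment is not shown. The special review covers ten completed waterbirths, against 124 planned for that arm, and looks at them after the birth. The Statistical Plan and Appendix D also have the investigators review adverse outcomes for all subjects, and the hospital's quality committee monitors all maternal and neonatal adverse outcomes.

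A reader might also want water inhalation, transfer to the warmer and temperature compared between arms. Water inhalation is undefined in the plan and has no counterpart in a birth on land. Transfer to the warmer may depend on the setting, since section V.C has the mother leave the tub for the third stage and allows the infant to be handed to staff meanwhile. Temperature is in neither the marker list nor the risk list.

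What survives the defence is that review of all subjects, and checking of entered data against source, do not ask about an event that has no field.

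**Conclusion.** The point holds as a gap in measurement. Respiratory distress is a marker and a risk by the protocol's own account, yet neither it nor resuscitation has a coded item, and the question that leads to the Other item is undefined. Followed as written, the plan cannot reliably report mild respiratory events in either arm, which weakens the open-ended part of Hypothesis 4a.

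The size cannot be taken from the documents. Under the assumed 5% to 10% rates, expected counts are about 4 to 7 in the water group and 2 to 4 in the land group, so a few unrecorded events would change the picture. Counts this small would support no firm comparison even with full capture.

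Unequal reporting between arms remains a possibility of unknown direction. The 1.8 ratio is an illustration with invented capture rates and is not evidence of bias. The change is worth making; the gap does not invalidate the trial or its coded neonatal outcomes.

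**What to change.** In Newborn variables (c), add two yes/no items, completed for every newborn in both arms whatever the answer to the general complications question:

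- Respiratory distress, defined by the signs already in section V.D: tachypnea above 60 per minute, grunting or retracting.
- Resuscitation given.

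Name both among the Hypothesis 4a outcomes. Suspected water inhalation may be added as a descriptive safety item, and first recorded temperature as an optional descriptive item, neither as a between-arm outcome for Hypothesis 4a. These are data items only and change no care.

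The cost is a small form change and a little more abstraction from the Epic record already in use, including back-filling past births where the information was charted. The limit should be stated: the items standardise abstraction, but they do not correct any difference between arms in what staff chart in the first place.

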## **VII. DATA COLLECTION**

- » From January 2022 through December 2025 eligible women will be offered study participation during routine prenatal care at 25 weeks 0 days to 34 weeks 0 days gestation. The study could be introduced to potentially eligible women in their second trimester. Several data elements will be reviewed and collected from the delivery record in Epic and the AUWMG midwifery database. REDCap will be utilized for data collection and storage for this study. Data collection will be completed by those listed on this study. After the first year of data collection, we plan to conduct an interim analysis and present year one preliminary data at a scientific meeting (Advocate Aurora Scientific Day 2023).

Variables to be collected at time of consent after coordinators have discussed participating in a randomized control trial:

- Do you wish to voluntarily participate in our randomized control trial that aims to evaluate maternal/neonatal outcomes associated with waterbirths, as well as your satisfaction with the birthing process? (0=No; 1=Yes)

Variables to be collected:

1. *Study related variables*
  - a. Medical reason/s participant becomes ineligible for waterbirth
    - i. Hep C positive (0=No; 1=Yes)
    - ii. Gestational age <37 or >42
    - iii. Non-vertex presentation (0=No; 1=Yes)
    - iv. Hypertensive (0=No; 1=Yes)
    - v. Febrile (0=No; 1=Yes)
    - vi. Category 2 or 3 fetal heart tones (0=No; 1=Yes)
    - vii. Amniotic sac is ruptured and fluid is not clear (0=No; 1=Yes)
    - viii. Other: notes
  - b. Maternal decision to withdraw participation (i.e. desire to leave the water): notes
2. *Maternal variables*
  - a. REDCap Record ID
  - b. Medical record number
  - c. Date of birth
  - d. BMI (kg/m^2) at initiation of prenatal care
    - a. Height (inches) and weight (lbs) at initiation of prenatal care
  - e. Race
  - f. Ethnicity
  - g. Education level
  - h. Marital status
  - i. Gravidity
  - j. Paritya
  - k. Date and time of admission
  - l. Date and time of delivery
  - m. Gestational age at time of delivery (WxDx)
  - n. Maternal position for birth:
    - a. upright (0=No; 1=Yes)
    - b. squatting (0=No; 1=Yes)
    - c. semi-sitting (0=No; 1=Yes)
    - d. left tilt (0=No; 1=Yes)
    - e. right tilt (0=No; 1=Yes)
    - f. hands and knees (0=No; 1=Yes)
    - g. standing (0=No; 1=Yes)
    - h. other (0=No; 1=Yes)
      - i. describe

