      - ii. Neonatal infection postpartum (0=No; 1=Yes)

1. If yes, follow-up comments
- iii. Other neonatal complications postpartum (0=No; 1=Yes)
  1. If yes, follow-up comments

This research study plans to store and manage the entire dataset in an AAH version of REDCap.

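### Newborn outcomes after discharge are recorded only for families reached at 4–8 weeks, with no vital-status item and no record check for the rest

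*Combined protocol and SAP*

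**What the plan says.** Item 3e of the newborn variables (VII. Data Collection) sets up a single contact after discharge: "At approximately 4-8 weeks postpartum, coordinator follow-up regarding newborn status (at postpartum visit or via phone call, etc". Its first field is "Were we able to touch base (0=No; 1=Yes" and its second is "If yes, were there any neonatal complications since discharge? (0=No; 1=Yes". Three outcomes follow for infants with complications: hospital admission, infection, and "Other neonatal complications postpartum (0=No; 1=Yes".

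The birth-stay items are separate. Apgar scores are item 3b. Item 3c, "Were there any newborn complications at time of birth? (0=No; 1=Yes", covers NICU admission, infection, injury, cord injury and a free-text other. None of these depends on the later contact.

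On sources, the same section says: "Several data elements will be reviewed and collected from the delivery record in Epic and the AUWMG midwifery database". It describes no later chart search. VIII. Potential Risks and Benefits names "rare adverse neonatal morbidity and mortality including neonatal death" among the neonatal risks, but the newborn variables contain no vital-status field.

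The safety hypothesis under Specific Aim 4 (4a) reads: "Infants in the waterbirth group will not experience more adverse outcomes (e.g., NICU admission, APGAR scores <7, umbilical cord injury, etc". It gives no time window. The Statistical Plan lists group tests and possible regressions. It has no rule for missing outcomes and none for which infants form the denominator.

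**The concern.** The 4–8 week contact is the only planned capture of newborn infection or readmission after discharge. If the form is followed as written, an infant whose family is not reached has no post-discharge outcome, even when a readmission sits in the Epic system the trial already uses. A death after discharge could be entered only under the other-complications item, which depends on the same contact.

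The background section treats the unknown neonatal risks as the most disputed aspect of waterbirth, and Aim 4 is a safety aim. With about 111 evaluable infants, delayed harms will be few, so one or two unrecorded events matter to how the result reads. Without contact numbers by arm, a reader could not judge how complete the post-discharge result is.

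**Working it through.** **Step 1: what is lost and what is kept for an unreached infant**

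| Outcome | Place in form | Depends on 4–8 week contact? |
|---|---|---|
| Apgar at 1 and 5 minutes | 3b | No |
| NICU admission, infection, injury, cord injury, other (at birth) | 3c | No |
| Any complication since discharge | 3e, second field | Yes, by its own wording |
| Admission, infection, other since discharge | 3e, third field | Yes, through the second field |
| Vital status | no field | Not applicable |

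The loss is confined to the post-discharge rows.

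**Step 2: inputs**

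The documents give no contact rate and no post-discharge event rate, so there is no stated figure to reproduce. The denominator is the plan's evaluable target, 74 waterbirth + 37 land = 111. As a check, 186 enrolled × (1 − 0.394) = 112.7, which agrees closely. The 39.4% is the rate of risking out, not of loss at 4–8 weeks, and is not used as a non-contact rate.

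Assumed for illustration: unreached fraction *u* = 0.2 to 0.4; ratio *k* of the event rate in unreached to reached infants = 1 or 2; event rate among reached infants = 3%.

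**Step 3: share of events unseen, and the true rate**

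Share unseen = uk / [(1 − u) + uk]. True rate = reached rate × [(1 − u) + uk].

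| u | k | Share unseen | True rate if 3.0% among reached |
|---|---|---|---|
| 0.2 | 1 | 0.2/1.0 = 20% | 3.0% |
| 0.4 | 1 | 0.4/1.0 = 40% | 3.0% |
| 0.2 | 2 | 0.4/1.2 = 33% | 3.0 × 1.2 = 3.6% |
| 0.4 | 2 | 0.8/1.4 = 57% | 3.0 × 1.4 = 4.2% |

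At k = 1 the rate among reached infants is unbiased; only the number of infants and events falls. At k = 2 the rate itself is too low.

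In counts over 111 infants: at k = 1, 111 × 0.03 = 3.3 events, of which 0.7 to 1.3 go unseen. At k = 2, 111 × 0.036 = 4.0 with 1.3 unseen, up to 111 × 0.042 = 4.7 with 2.7 unseen. That is roughly one to three infants across both arms.

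**Step 4: precision**

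With no events seen in n infants, the one-sided 95% upper bound on the event rate is 1 − 0.05^(1/n).

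| Unreached | Waterbirth n | Bound | Land n | Bound |
|---|---|---|---|---|
| 0% | 74 | 4.0% | 37 | 7.8% |
| 20% | 59 | 5.0% | 30 | 9.5% |
| 40% | 44 | 6.6% | 22 | 12.7% |

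**Step 5: between-arm direction**

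If u and k are the same in both arms, each arm's rate is multiplied by the same factor and their ratio is unchanged. The ratio moves only if u or k differs by arm, and its direction depends on which arm has the larger factor. The documents give neither quantity by arm.

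**The case against.** Several stronger readings are tempting, and the documents do not support them.

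- A reader might infer that unreached infants drop out of Hypothesis 4a altogether. They do not. The outcomes 4a names are birth-stay items kept for these infants. Whether the 4–8 week items belong to 4a is not stated: its list is open-ended and has no time window.
- A reader might infer that any infant death would go unrecorded. A death during the birth stay can be entered as another complication at birth, and a later one under the other item if the family is reached. The data safety monitoring plan also has the investigators review all adverse outcomes and report adverse events to the IRB. A hospital committee covers events at the facility, and adverse outcomes are logged. These are real safety routes. However, none is described as feeding the analysis dataset, and checking entered data against source is not a search for events never entered.
- A reader might infer that the gap favors a finding of no excess harm with waterbirth. Contact could differ by arm in an unblinded trial, but nothing in the documents says that it does or in which direction.

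It can also be said that only the second field of 3e carries an explicit contact condition, that the REDCap branching is not shown, and that IV. Study Design names Epic as a general source. So later chart entry is unstated rather than forbidden. That is fair, but the third field still hangs on the answer to the second, and no step directs anyone to the chart when contact fails.

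Finally, this is a secondary outcome in a pilot, and the likely number of missed events is small. That bears on priority, not on whether the gap exists.

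**Conclusion.** The point holds for the post-discharge component only. As written, newborn admission, infection and other complications after discharge are known only for reached families, and no vital-status item, record check or rule covers the rest. Events already in the hospital's own record can be lost to the comparison.

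The size cannot be fixed from the documents. All the percentages in the working rest on assumed non-contact of 20–40%, an assumed equal or doubled risk, and an assumed 3% rate among reached infants. Only the doubled-risk case gives an understated rate; the equal-risk case is a loss of precision. The direction of any bias between arms is unknown.

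This is a cheap improvement to data capture and does not touch clinical management. The rule in IV. Study Design that no further data are collected once a participant becomes ineligible is a separate, possibly larger, loss of newborn data, and this point does not address it.

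**What to change.** In item 3e:

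1. Remove the contact condition from the admission, infection and other items, and add newborn vital status.
2. At the end of the 4–8 week window, check Epic for every infant still in the study, whether or not the family was reached. Record the source of each answer: chart, contact or both.
3. For an unreached infant with no charted event, record a distinct code meaning none in chart, not contacted. Do not enter 0, which would turn missing information into a false negative.
4. Report by arm the numbers reached, chart-only, and with neither.
5. Compare chart-found events across all infants still in the study, so that both arms rest on the same source. Show the comparison among reached families alongside it.

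It would also help to state whether the 4–8 week items form part of Hypothesis 4a.

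The cost is a few REDCap fields and a short chart check by the existing coordinator for the infants still in the study (about 111 at the planned evaluable size). Events already charted for past participants still in the study can be recovered the same way. The remaining limit is that care given outside the health system stays unseen for unreached families, so some under-count will persist and should be stated with the result.
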